Randomized trials on apps that follow the US Clinical Practice Guidelines (USCPG) begin to address that research gap. But only following the USCPG has had limitations in other modalities of delivery [9-15]. An approach, called Acceptance & Commitment Therapy (ACT), addresses these limitations with both innovative intervention content and highly promising results from six published trials [16-21]. ACT's innovation is its dual focus on increasing willingness to experience physical cravings, emotions, and thoughts that cue smoking while making values-guided committed behavior changes [22]. We recently developed the first ACT app for smoking cessation, called "SmartQuit," and tested it in a pilot randomized controlled trial (N = 196), comparing it with an app that follows USCPG (National Cancer Institute's "QuitGuide"). The trial design was proven feasible, with successful national recruitment (N = 196 recruited in 10 weeks) and strong outcome survey completion rate (84%). Results showed that SmartQuit had: (1) higher participant engagement and satisfaction than QuitGuide, (2) higher levels of acceptance of cravings than QuitGuide, and (3) descriptively higher quit rates (albeit non-significant) than QuitGuide at the two-month follow-up [21]. Building on these promising results, we propose a fully-powered, randomized controlled trial that compares a refined version of SmartQuit, called iCanQuit to QuitGuide, which follows the USCPG, to definitively determine whether an ACT app is more efficacious than a USCPG app. Thus we propose the following Specific Aims:

Aim 1. Determine whether iCanQuit produces significantly higher abstinence than QuitGuide. **Primary endpoint:** 30-day point prevalence abstinence at 12 months post-randomization. Importance of this aim: will determine the quit rates with precision and whether iCanQuit provides more robust quit rates than QuitGuide.

Aim 2. Determine whether the iCanQuit (but not the QuitGuide) smoking cessation outcomes are mediated by these psychological processes central to the theoretical model underlying ACT: commitment to quitting and acceptance of internal (a) sensations, (b) emotions, and (c) thoughts that cue smoking. Importance of this aim: will identify ACT processes needing further targeting, and determine whether iCanQuit, but not QuitGuide, operates through ACT-specific theoretical processes.

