Aim 2: ACT Mediators. Acceptance of internal cues to smoke: Measured using the Avoidance and Inflexibility Scale (AIS; $\alpha = .93$; [16, 20], which assesses one's willingness to experience sensations (9 items), emotions (9 items), and thoughts (9 items) that cue smoking. A sample item for the sensations scale is: "To what degree did you allow yourself to have urges to smoke?" Commitment to quitting. Commitment to quitting despite internal (e.g., cravings, anxiety) and external (e.g., smoking in the social environment) cues to smoke will be measured using the Commitment to Quitting Scale (CQS; $\alpha = .93$; [59]). Sample item: "No matter how many people around me smoke, I won't let myself smoke once I quit." Regarding assessment timing, three months post randomization is when we expect acceptance and commitment to increase the most, as consistent with past ACT smoking cessation studies [16, 17, 20, 82], and would allow testing of our hypothesized model of increases in acceptance and commitment at three months mediating the impact of the intervention on smoking cessation by twelve months.

Aim 3: Costs of delivery, for cost-effectiveness analyses. Costs associated with each app's delivery include the cost to: (1) host the servers and databases, (2) conduct software updates to accommodate ongoing changes in operating systems, (3) have programming staff to answer technical questions, and (4) cost of facilities and equipment needed to maintain each (e.g., office space for personnel, computers). NCI, the host of QuitGuide, has agreed to provide these costs for QuitGuide [32]. Research-related costs will not be included.

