Analyses. Aim 1. Our primary outcome hypothesis is that iCanQuit will have significantly higher 30-day point prevalence abstinence at 12 months post-randomization than QuitGuide. **Analyses:** For each comparison of the arms on the primary and all secondary endpoints, we will use a logistic regression model with complete case smoking cessation outcome [9-14]. The model will adjust for all stratification factors as well as baseline factors that might be imbalanced after randomization. In addition, we will conduct these analyses: (1) multiple imputation of missing outcomes [90-92], (2) missing equals smoking outcomes [9-14], (3) using a secondary cessation outcome of no use of cigarettes **and** other nicotine or tobacco products except FDA-approved nicotine replacement therapies. Finally, we will compare the two arms on utilization of their assigned app.

Aim 2. We hypothesize that the iCanQuit arm's (but not the QuitGuide arm's) smoking cessation outcomes will be strongly mediated by these psychological measures that are central to the theoretical model underlying ACT: commitment to quitting and acceptance of internal (a) sensations, (b) emotions, and (c) thoughts that cue smoking. This hypothesis is consistent the ACT model and prior ACT for smoking cessation intervention studies [16, 17, 20, 82]. **Analyses:** For each mediator, the model is expressed as three regression equations that relate the main independent variable X

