(ACT intervention), the mediator M (change from baseline to 3-months post randomization in the acceptance variable, and/or commitment to quitting smoking despite internal cues), and the binary endpoint Y at 12-months post-randomization (e.g., 30-day abstinence). The first regression describes the total intervention effect (X) on the outcome (Y): $\text{logit}(Y) = \gamma_1 + \tau X$, where the parameter τ measures the total intervention effect. The second regression describes the impact of the intervention (X) on the mediator (M): $M = \gamma_2 + \alpha X$. The third regression describes the simultaneous impacts of the intervention (X) and mediator (M) on the outcome (Y): $\text{logit}(Y) = \gamma_3 + \tau'X + \beta M$. Since the endpoint is binary, the mediation effect is the product term $\alpha\beta$, whose empirical distribution will be estimated via 5000 bootstrapped samples. Bootstrapping is a resampling method which provides a powerful test of mediation that does not rely on normality assumptions [93-95]. Randomization should remove potential confounding effects [92, 93], and if needed, we will adjust each model by covariates that differ at baseline or predict outcome. Following VanderWeele and Preacher methods [94, 95], we will also explore any interactions between mediators and treatment arm. And we will explore whether utilization of assigned app and usage of cessation pharmacotherapy mediates cessation outcomes.

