For Primary Aim 1, projected quit rates at 12 month follow-up were conservatively calculated using (1) quit rates at two-month follow-up in our pilot RCT (which used methods similar to this proposed R01) and (2) well-established relapse curves, which provide a data-derived estimate of the rate of decay of 2-month intervention effects by 12 month follow-up [60, 76, 77]. Specifically, the estimates account for a quit rate reduction from the observed two-month 13% quit rate in the pilot to an estimated 11% 12-month quit rate for ACT and from the observed two-month 8% quit rate in the pilot to an estimated 7% 12-month quit rate for QuitGuide. These reduction estimates are consistent with the relapse rates observed by 12 month follow-up [60, 76, 77]. Having 80% two-tailed power to significantly detect a quit rate as low as 11% for iCanQuit (vs. 7% for QuitGuide) required a sample size of 1622. However, we set the target recruitment to 2500 participants for the Exploratory Aim analyses.

For Primary Aim 2, regarding the acceptance mediators, we estimated that they would explain at least 60% of ACT's effect on quitting smoking, as based on prior trials [16, 17, 20, 82]. For the commitment to quitting mediator, we estimated that it would explain at least 25% of ACT's effect on quitting smoking, as based on prior trials [16, 17, 20, 82]. The 5000 iterative simulations showed that a sample size of 811 per arm would provide high power (>99%) to detect the estimated mediation effects for acceptance and commitment.

PROTECTION OF HUMAN SUBJECTS

All procedures for this study will be reviewed by Fred Hutch's IRB prior to human subjects' participation. Based on our prior history with the pilot randomized trial which motivated this proposed trial, we expect no problems obtaining IRB approval.

Experimental design

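### Aim 2's one-mediator-at-a-time models cannot tell apart correlated processes that the app moves together; add a joint mediator model

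*Combined protocol and SAP*

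**What the plan says.** The Aim 2 hypothesis (Analyses, Aim 2) names four mediators: "commitment to quitting and acceptance of internal (a) sensations, (b) emotions, and (c) thoughts that cue smoking". The acceptance measure (Primary assessments, Aim 2: ACT Mediators) is one instrument "which assesses one's willingness to experience sensations (9 items), emotions (9 items), and thoughts (9 items) that cue smoking". Commitment is measured on a separate scale.

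The analysis is set out per mediator: "For each mediator, the model is expressed as three regression equations that relate the main independent variable X". The outcome equation contains treatment arm, one M and one slope β. The mediated effect is the product αβ, tested with 5000 bootstrap samples. M is the baseline to 3-month change "in the acceptance variable, and/or commitment to quitting smoking despite internal cues". No equation is written with two or more mediators, no contrast between indirect effects is planned, and no rule covers the case where all four are significant. Covariate adjustment is allowed where needed, but the other mediators are not named as covariates.

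Specific Aims gives one purpose of Aim 2 as follows: it "will identify ACT processes needing further targeting". The other purpose is to show whether iCanQuit, but not QuitGuide, works through ACT-specific processes.

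For the acceptance mediators, the Power section assumes that "they would explain at least 60% of" the ACT effect. It assumes at least 25% for commitment, and reports more than 99% power at 811 per arm.

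**The concern.** Saying which process needs targeting means telling processes apart. Suppose one acceptance subscale drives quitting and another does nothing but is correlated with the first. In a model holding only the inert subscale, its slope β picks up the active subscale's effect. If the app has also moved the inert subscale, α is non-zero too, so αβ is non-zero and tests as mediation.

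Both conditions are plausible here. Three of the mediators are parts of one questionnaire. The plan expects acceptance and commitment both to rise by three months and hypothesises that all four mediate. The likely output is then four significant mediators, with no means of saying which did the work. App content could be redirected towards a process that contributes nothing.

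**Working it through.** **Inputs from the documents.** Quit rates 11% and 7%; total N 1622 (811 per arm); two-sided 0.05; shares mediated 60% and 25%; 84% retention of 1250 per arm, i.e. 1250 × 0.84 = 1050.

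**Assumed, because the documents do not give them.** App effect on each mediator (0.3 SD unless stated) and the correlations between mediators (0 to 0.9).

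**The plan's own figures first.**
- The two-proportion formula without continuity correction gives 803 per arm, 1606 in total. This is 16/1622 = 1.0% below the stated N. Power at 811 per arm is 80.4%.
- Total effect on the log-odds scale: ln(0.11/0.89) − ln(0.07/0.93) = 0.496.
- Simulated single-mediator power exceeds 99% for both shares at shifts of 0.25 and 0.30 SD. At 0.20 SD it is 97–98%, and at 0.15 SD 82–83%. For the 25% mediator it is 94% at 0.4 SD and 81% at 0.5 SD. The stated figure is therefore reproducible, but only for some mediator shifts.

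**Expected size of the borrowed effect.** With a 60% share and a 0.3 SD shift, the active slope is 0.60 × 0.496 / 0.3 = 0.992 per SD. An inert mediator at within-arm correlation ρ, alone in the model, takes a slope of roughly ρ × 0.992. Its apparent share is then roughly 0.3 × ρ × 0.992 / 0.496 = 0.60ρ.

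**Simulation.** Four mediators, only one active (60%), all moved 0.3 SD, 811 per arm, 600 replicates. The interval for αβ came from Monte Carlo draws of the product, in place of the 5000-sample bootstrap. Results for an inert acceptance subscale:

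| Correlation with the active subscale | 0.60ρ | Share credited, single model | Flagged, single model | Flagged, joint model |
|---|---|---|---|---|
| 0 | 0% | about 0% | 4–6% | 4–6% |
| 0.3 | 18% | 17% | 89% | 5–6% |
| 0.5 | 30% | 28% | 99.8–100% | 5–6% |
| 0.7 | 42% | 40% | 100% | 4–5% |
| 0.8 | 48% | 46% | 100% | 5–6% |

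- Inert commitment at correlation 0.3 with the active subscale is flagged in about 88–90% of single-model runs. Across all settings at 811 per arm the joint model flags inert mediators in 4–8% of runs.
- At 1050 per arm the single-model error is 94–96% at correlation 0.3 and 100% for subscales at 0.5 and above.
- **Limiting condition:** an inert subscale that the app does not move is flagged in 4–5% of runs even at correlation 0.8. One moved by 0.15 SD is flagged in about 85%.
- If the active mediator carries only 25%, inert subscales are flagged in 68–69% of runs at 0.5 and 96–97% at 0.8.

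**Power of the joint model.** In the 60% setting, power for the active mediator is 100% up to correlation 0.8 and 98.5% at 0.9. If the active mediator carries 25%, power is 98% at 0.5 and 73% at 0.8, against 99.7% in the single model. If all three subscales are active at 20% each (commitment inert, correlated 0.5 with them), power per subscale is about 80–85% at 0.5, 64–68% at 0.7 and 42–50% at 0.82. All three are detected in about 50–55%, 17.5% and 1% of runs.

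**What the 60% means.** If it applies to each subscale, the assumed shares sum to 60 + 60 + 60 + 25 = 205%, which is possible only if they overlap. If it applies to acceptance as a whole, the sum is 60 + 25 = 85%.

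**The case against.** Four counter-arguments carry weight.

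- **No correlation is documented.** A reader might infer that all four mediators are strongly related. That is plausible for three parts of one scale, but the documents give no correlation, M is a change score, and commitment is a separate instrument. A value of 0.82 between subscales can be derived from the reported alpha of .93 if that alpha is for all 27 items and the items correlate equally: mean inter-item r = .93/(27 − .93 × 26) = 0.330, and 81 × 0.330/(9 + 72 × 0.330) = 0.82. The same assumption makes the reliability of a 9-item subscale 9 × 0.330/(1 + 8 × 0.330) = 0.82. The error-corrected correlation is then 1, so the subscales measure one construct and there is nothing to separate. The value is not evidence for the size of the problem, and serves above only as a demanding case for joint-model power.
- **The aim does not fail outright.** A reader might conclude that Aim 2 cannot be met. The documents do not support that. Single models can still show that acceptance as a whole mediates, and can drop processes the app does not move. The ACT-specific purpose is a separate question. The and/or in the definition of M leaves a combined model possible, though unspecified.
- **No ranking or adding of shares is planned.** The planned output is αβ; percentages appear only as power assumptions. The reference list includes a methods paper whose title covers several mediators (reference 95), but it is cited for bootstrapping and mediator-by-arm interactions, so its citation shows no departure from method.
- **A joint model can miss real processes.** When all three subscales are active, it often fails to detect them individually.

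All four stand as limits. They do not remove the gap: the written equations cannot separate processes that move together, and a correlation of 0.3 is enough to matter.

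**Conclusion.** The point holds in limited form. As written, Aim 2 cannot distinguish mediators that are correlated and that the app moves together, so it cannot fully support its stated purpose of identifying which processes to target. Under the assumptions above (0.3 SD shift in each mediator, 811 per arm, one active mediator at 60%), the false-mediator rate is about 90% at correlation 0.3 and about 100% at 0.5 or above. The share wrongly credited is about 17% and 28% at those correlations. Without an app effect on the inert process the error stays near 5%.

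These figures further assume normally distributed mediators and no unmeasured mediator–outcome confounding, with Monte Carlo error of about 1–2 percentage points. This is a worthwhile, inexpensive improvement to a mechanism aim. It does not affect the primary comparison in Aim 1.

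**What to change.** In Analyses, Aim 2:

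1. Keep the single-mediator models and pre-specify beside them one joint outcome model: logit(Y) = γ + τ′X + β1·sensations + β2·emotions + β3·thoughts + β4·commitment.
2. Report the total indirect effect, the combined acceptance indirect effect, each specific indirect effect, and contrasts between them, all with bootstrap intervals.
3. State that the single-mediator models alone will not be used to claim that one process rather than another mediates.
4. State that a non-significant specific effect in the joint model will not be read as proof that a process is inactive.

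In Power, Aim 2: say whether the 60% is per subscale or for acceptance as a whole; say that the more than 99% power applies to the single-mediator tests; and give joint-model power over a stated range of correlations and mediator shifts.

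The cost is some extra analysis and a power simulation, with no new data collection. The downside is wider intervals for the specific effects. With three subscales correlated 0.82, the variance inflation is 1/(1 − 2ρ²/(1 + ρ)), about 3.7, so standard errors are about 1.9 times as large. That is why the combined acceptance effect and the contrasts should be reported with the specific effects.

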Aim 3. Determine whether iCanQuit is significantly more cost-effective than QuitGuide, as measured by cost per additional quitter, incremental cost-effectiveness ratio (ICER), and incremental cost per quality-adjusted life year (QALY). Importance of

this aim: will provide payers (e.g., insurance companies) and policymakers results needed to decide whether to adopt iCanQuit.

[figure not shown]
Exploratory Aim: Explore whether iCanQuit, as compared to QuitGuide, has higher quit rates for those with these baseline factors: (a) low acceptance of sensations, emotions, and thoughts that cue smoking, (b) heavy smoking (≥ 20 cigarettes/day), (c) current mental health symptoms, and (d) being racial/ethnic minority. Importance of this aim: will potentially identify key subgroups that benefit most from iCanQuit, and thereby aid in reducing tobacco-related health disparities.

Innovations. (1) ACT's innovative features augment the US Clinical Practice Guidelines; (2) ACT follows an innovative theory: Relational Frame Theory; (3) ACT on the smartphone is novel; (4) First randomized trial of a smartphone app for adult smoking cessation; (5) The first time that the following have been tested for **any** behavior outcome: (a) ACT delivered via smartphone, (b) mediation of the effects of a smartphone app, (c) cost-effectiveness of a smartphone app, and (d) exploration of subgroups who benefit most from a smartphone app. While there are thousands of apps and hundreds for smoking [2], testing an app's efficacy is scientifically innovative. That's a critical gap this application fills.

Approach

Randomized trial experimental design. We will conduct a fully-powered two-arm randomized controlled trial that compares iCanQuit to QuitGuide, which follows the USCPG. To balance baseline variables between the two conditions, we will stratify randomization by daily smoking frequency (≤ 20 vs. ≥ 21), education (\leq high school vs. \geq some college), race/ethnicity (minority race/ethnicity vs. non-Hispanic White) and depression screen (CES-D score ≤ 15 vs. ≥ 16). Moderators will be measured at baseline. Mediators will be measured at baseline and three months post randomization. Consistent with cessation trial designs [60], cessation and cost-effectiveness outcomes will be measured at 3, 6, and 12 months post randomization.

Figure 1. Experimental Design

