
Exploratory Aim. This aim will explore whether iCanQuit, as compared to QuitGuide, has higher quit rates for those with these baseline factors: (a) those scoring low on acceptance of sensations, emotions, and thoughts that cue smoking, (b) heavy smokers (≥ 20 cigarettes/day), (c) smokers screening positive for mental health symptoms, and (d) being a racial/ethnic minority. **Analyses:** This aim will explore key moderators of ACT treatment outcomes and aid in the critical effort to improve quit rates for these high-risk groups [101-105]. The ACT model suggests that, in addition to being a key mechanism (i.e., mediator) of treatment, baseline acceptance is a moderator of treatment outcome [22]. Specifically, we hypothesize that people who avoid their

triggers to smoke (i.e., low acceptance) will benefit most from ACT because ACT teaches skills to overcome avoidance. We also hypothesize that this focus on acceptance may be especially helpful for heavy smokers and those with mental health symptoms because physical, emotional, and cognitive cues to smoke are stronger for these individuals [106-109]. Finally, testing moderation by race/ethnicity will allow us to generate hypotheses about whether minorities overall respond differently to ACT than non-Hispanic Caucasians. We will explore moderation with separate logistic regression models for each moderator variable, where 30-day abstinence at 12-months post randomization is the outcome (Y). The model will include the moderator (Z), group assignment (X), and an interaction between moderator and group assignment (X*Z). Statistically significant interactions will be assessed with plots showing how the slope of Y on X is dependent on the value of Z. The slopes will be derived from logistic regressions that correspond to the prediction of Y from X at a single value of moderator Z.

Power. We determined sample size with 5,000 iterative simulations aimed at 80% power for Primary Aim 1. We used the following parameters: (1) participants randomized to one of the two arms; (2) two-sided test with $\alpha = .05$; (3) intent-to-treat analysis where, as standard in smoking cessation trials, all those with missing data are coded as smokers [11, 60]. The calculations do not account for potentially higher effect sizes from the adjustment of stratification factors.

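### Aim 2 scores each mediator as a raw change and leaves adjustment for its baseline score to a conditional clause, so the commitment indirect effect may be understated if the month-3 level drives quitting

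*Combined protocol and SAP*

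**What the plan says.** Under Analyses, Aim 2, the mediator is defined as "the mediator M (change from baseline to 3-months post randomization in the acceptance variable", with commitment to quitting treated the same way. The mediator equation is M on arm: M = γ2 + αX. The outcome equation is logit(Y) on arm and mediator: γ3 + τ'X + βM. Neither contains a baseline mediator score. The plan then states that "the mediation effect is the product term $\alpha\beta$, whose empirical distribution will be estimated via 5000 bootstrapped samples".

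The same paragraph relies on randomization against confounding and adds: "if needed, we will adjust each model by covariates that differ at baseline or predict outcome". It names no covariate and gives no selection threshold.

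Three other places bear on this:
- The experimental design says "Mediators will be measured at baseline and three months post randomization", so baseline scores are available.
- The Exploratory Aim says that "baseline acceptance is a moderator of treatment outcome".
- The Power section expects acceptance to explain at least 60% of the effect and commitment at least 25%, and states that "a sample size of 811 per arm would provide high power (>99%) to detect the estimated mediation effects for acceptance and commitment".

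**The concern.** A change score contains its own baseline with a minus sign. Suppose quitting at 12 months depends on how accepting or committed a person is at month 3, wherever they started. Then part of the variation in the change score is baseline variation that pulls the wrong way, and the slope β on an unadjusted change score is biased. Randomization does not prevent this. It protects α and the total effect, but the bias in β comes from how M is scored and would occur with perfectly balanced arms.

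Aim 2 is meant to say how much of the effect of iCanQuit runs through each ACT process. If baseline is left out when it is needed, a process can look less important than it is. Whether that happens would depend on an adjustment decided after the data are seen.

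**Working it through.** **Plan's own figures.** For 11% vs 7%, two-sided 0.05 and 80% power, the usual two-proportion formula (pooled variance, no continuity correction) gives 803 per arm, 1606 in total. The plan has 1622 by simulation, and 811 per arm gives 80.4% power, so the figure is reproduced. The stated >99% for mediation cannot be reproduced uniquely, because the plan fixes only the share mediated (the product αβ), not α and β separately.

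**Inputs from the plan.** Total log odds ratio = ln(0.11/0.89) − ln(0.07/0.93) = 0.496. A 60% share is αβ = 0.298; a 25% share is αβ = 0.124.

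**Assumptions (not in the documents).** Baseline to month-3 correlation r; SD ratio k = SD(month 3)/SD(baseline); arm effect α in SD units; quitting driven by the month-3 level.

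**Step 1: bias of the displayed model.** With D = M3 − M0, the slope on D is β multiplied by

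cov(M3, D)/var(D) = (k² − rk)/(k² + 1 − 2rk).

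At k = 1 this is (1 − r)/(2 − 2r) = 0.50 for every r. Otherwise:

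| k | r = 0.2 | r = 0.5 | r = 0.8 |
|---|---|---|---|
| 0.8 | 0.36 | 0.29 | 0.00 |
| 1.0 | 0.50 | 0.50 | 0.50 |
| 1.2 | 0.61 | 0.68 | 0.92 |
| 1.5 | 0.74 | 0.86 | 1.24 |
| 2.0 | 0.86 | 1.00 | 1.33 |

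α is unchanged in expectation. Large-sample logistic simulation at k = 1 agrees: αβ is about 0.48 of truth at r = 0.3, 0.5 and 0.7. Adding the baseline score restores it to about 0.30, against a true 0.298.

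**Step 2: what the covariate clause repairs.** Take the clause to mean that baseline enters if it predicts outcome at p<0.05 (my threshold; the plan states none). With β = αβ/α, the chance of entry is about Φ(r·β·√(N × 0.09 × 0.91) − 1.96). For N = 1622 the square root is 11.53.

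Commitment, r = 0.5, k = 1:
- 0.2 SD: β = 0.620; Φ(3.57 − 1.96) = 0.95
- 0.3 SD: β = 0.413; Φ(2.38 − 1.96) = 0.66
- 0.4 SD: β = 0.310; Φ(1.79 − 1.96) = 0.43

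Simulation gives about 93%, 64% and 42%. The αβ that results from applying the clause, as a fraction of truth, is:

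| Mediator, n per arm | r | 0.2 SD | 0.3 SD | 0.4 SD |
|---|---|---|---|---|
| Commitment, 811 | 0.5 | 0.99 | 0.86 | 0.77 |
| Commitment, 811 | 0.3 | – | 0.66 | – |
| Commitment, 1250 | 0.5 | 0.99 | 0.94 | 0.85 |

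A rough check is entry × 1 + (1 − entry) × 0.5, which for the first row gives 0.97, 0.83 and 0.72. The simulated values are a little higher because trials that fail the screen tend to be those where baseline happens to be weakly related to outcome, so less bias arises.

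For acceptance (60%) at 811 per arm and r = 0.5, baseline enters in 99–100% of trials and αβ is 0.99–1.00 of truth. At r = 0.3 with a 0.5 SD arm effect, entry drops to about 58%, so even there the repair is not certain.

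**Step 3: if change is the driver.** Both models recover the true share. Adding baseline then costs some precision in β: in the runs made, at most 6 to 8 points of power, for example 93% to 87% for commitment at 0.4 SD and 811 per arm.

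**The case against.** The strongest reply is that the plan already allows the adjustment. In the scenario where harm arises, baseline does predict outcome, so the clause would often bring it in. This stands for acceptance at moderate correlation. It stands only in part for commitment, where the outcome of a significance screen would decide which model is reported.

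Second, the level-driven mechanism is an assumption. The section on ACT mediators speaks of increases at three months mediating later cessation, and under that reading the displayed model is not biased in this way. That is correct. But the displayed model imposes the change mechanism, whereas the adjusted model contains it as a special case (coefficient on baseline equal to minus β). The Exploratory Aim's statement that baseline acceptance is a moderator shows that the authors expect baseline to matter. It concerns an interaction, though, and is not evidence that the month-3 level drives quitting.

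Third, the trial plans 1250 per arm, not 811. The shortfall is then smaller (third row of the second table).

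Two stronger readings are tempting and unsupported. A reader might infer that Aim 2 as written reports half the mediated share. That needs equal SDs, a level-driven mechanism and a clause that is never applied, and the documents establish none of these. A reader might also infer that change scoring explains a failure of the >99% power statement. With baseline included, commitment power still falls to about 86% at an assumed 0.4 SD, and the plan does not give α and β separately, so any failure cannot be pinned on the scoring.

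**Conclusion.** The point holds as a gap in prespecification. The displayed equations omit the baseline mediator score, and its inclusion is left to an unspecified conditional rule. If the month-3 level drives quitting and the SDs are equal, the likely consequence is a commitment αβ of about 0.77 to 0.99 of truth at 811 per arm and r = 0.5 (0.85 to 0.99 at 1250 per arm). It is about 0.66 at 811 per arm with r = 0.3 and a 0.3 SD arm effect. Acceptance is usually unaffected. With unequal SDs the unadjusted bias can be smaller, larger or reversed. If change drives quitting, there is none. These sizes rest on an assumed p<0.05 screen, assumed arm effects, correlations and SDs, and no dropout. The primary endpoint analysis is not touched. I would label this a cheap improvement.

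**What to change.** In Analyses, Aim 2, state that the baseline score of the same mediator scale is always a covariate in both the mediator equation and the outcome equation, and that αβ is bootstrapped from those models:

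- M = γ2 + αX + δM0
- logit(Y) = γ3 + τ'X + βM + κM0

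M need not be redefined. Since βM3 + κM0 = β(M3 − M0) + (κ + β)M0, coding M as the change or as the 3-month score gives the same β. In the mediator equation only δ shifts, by 1, so α is the same too. The conditional clause can remain for other covariates.

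The cost is a sentence of wording; both scales are already scheduled at baseline and month 3. One gain is that α becomes more precise: its variance is proportional to 1 − r² instead of 2(1 − r), which at r = 0.5 and 811 per arm is an SE of 0.0430 against 0.0497. The downside is the loss of up to 6 to 8 points of power if change alone is the driver.
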